Enhancing Well-Being Through Exercise During Older Age

NCT04536727

1/23/2019

“Enhancing Well-Being Through Exercise During Older Age”

Principal Investigator:

[name]
[contact]

Sponsors:

The Midwest Roybal Center for Health Promotion and Translation Pilot Grant Program

Study Locations:

The University of Illinois at Chicago
[name]

Oakwood Shores
[name]

Table of Contents

	Page
Table of Contents.....	2
A. Specific Aims.....	3
B. Background and Significance.....	3
C. Research and Design Methods.....	4
D. Protection of Human Subjects.....	11
Citations.....	14
Table 1.....	16

Research Protocol for “Enhancing Well-Being Through Exercise During Older Age”

Primary Investigator: [name]

Sponsor: The Midwest Roybal Center for Health Promotion and Translation Pilot Grant Program
Protocol Version 22

1/23/2019

A. Specific Aims

AIM 1. Determine the feasibility of adapting Fit and Strong! to include affect and mood-related content and employing this intervention among older adults with a range of depressive symptoms.

HYPOTHESIS 1. Participants will demonstrate **(1a)** adherence to the Fit & Strong! intervention defined as attendance at two-thirds or more of the exercise sessions over a 8-week period and **(1b)** acceptability of the Fit & Strong! intervention as a way to reduce depressive symptoms and improve positive affect and reduce negative affect, defined as at least 75% of participants reporting positive subjective opinions of the protocol during debriefing session assessments.

AIM 2. Begin to determine whether Fit & Strong! is efficacious as an approach for reducing depressive symptoms and improving positive affect and reducing negative affect among older adults.

HYPOTHESIS 2. Compared to wait-list participants, intervention participants will report an improvement in positive affect and a reduction in negative affect and depressive symptoms at 9 weeks as measured by medium to large effect sizes.

AIM 3. We will explore the relationship between negative/positive affect and depressive symptoms and maintenance of physical activity between groups at baseline, and 9- weeks, in order to determine whether an improvement in positive affect and a reduction in positive affect is associated with an increase in physical activity.

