HYPOTHESIS 3. Participants randomly assigned to the intervention arm will demonstrate an increase in physical activity at 9- weeks as measured by medium to large effect sizes, and this increase in positive affect/reduction in negative affect will be mediated by an increase in physical activity.

AIM 4. We will explore the relationship between physical activity and the brain between groups at baseline and 9-weeks, in order to determine whether an improvement in brain network connectivity and function is associated with an increase in physical activity.

HYPOTHESIS 4. Participants randomly assigned to the intervention arm will demonstrate an increase in physical activity and brain network connectivity and function at 9-weeks.

B. Background and Significance

Affective well-being is typically characterized as the presence of positive feelings and the absence of negative feelings over time, and have been showing to be relatively independent constructs (Lucas et al., 1996). After the age of 60, negative affect tends to remain stable, (Gross et al., 1997) but positive affect decreases (Kunzmann et al., 2000). Positive affect in late life has been positively associated with social engagement (e.g., Kunzmann, 2008), while negative affect in late life has been linked to self-reported physical health (e.g., Brief et al., 1993). Studies have demonstrated that exercise is associated with higher positive affect and lower negative affect (Dua et al., 1992; Rizk et al., 2015) In clinical samples, exercise has long been established as an

[figure not shown]

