effective treatment for depression in younger [Krogh et al., 2011] and older adults [Blake et al., 2009]. Importantly, exercise also addresses vascular risk factors thought to be particularly relevant to aging (Blaha et al., 2016), in general, as well as depression in late life [Alexopoulos et al., 2006, Sheline et al., 2010]. While there have been several studies demonstrating the benefits of exercise on depression in older adults, no known study has examined the positive benefits of a structured, group exercise program on mood and well-being in an aging sample. As an ancillary aim, we will also examine the impact of a structured exercise intervention on cognitive functioning. Fit and Strong!, a physical activity / behavior change program for older adults with lower extremity osteoarthritis, has demonstrated efficacy, effectiveness, and ease of dissemination for individuals with osteoarthritis living in the community [Hughes et al., 2004, 2006, 2010]. The goal of this study is to adapt Fit & Strong! for increasing positive affect and reducing negative affect and depressive symptoms among older adults residing in the community.

C. Research Design and Methods

C.1 General study design

We will enroll 40 subjects in this study between the ages of 60 and older, from the community who score at least 1 on the Patient Health Questionnaire-8 (PHQ). Up to 20 participants will have PHQ-8 scores of 1-4, while up to one-half of participants will have PHQ scores >4. At the outset of the study, up to 20 individuals will be randomly assigned to the intervention portion of the study, while up to 20 individuals will be randomly assigned to a crossover wait-list group, who will undergo the intervention beginning at study week 10. Outcome measures will be administered to all participants before the intervention and to the intervention group after they undergo the intervention. The wait-list group will complete all of their outcome measures before they begin the intervention(see Figure 1).

Figure 1

C.2 Phone screen and Study Visits

C2.1 Pre-Study Screen:

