machine will produce imaging of each participant's brain. Participants will be allowed to request earplugs to wear during the procedure, as the machine is quite noisy. In the case that a participant should start to feel claustrophobic, the MRI testing will be stopped immediately. The total time each participant will be asked to stay inside the machine should be no more than an hour. MRI testing will take place at baseline before the exercise intervention and after the intervention (week 9). A taxi will be provided to and from the imaging center for participants that need it. Participants will be paid \$50 at each session (\$100 total).

C 6.7. Data Analysis/Interpretation: Participation rates and program acceptability ratings will be quantified. Changes in depressive symptoms and positive and negative affect will be analyzed using a repeated measures ANOVA model. Between-group analyses will be conducted to determine whether significant changes occur in the outcomes between baseline, 9- and 18-weeks to examine maintenance effects over time. A mixed-effects model will be used to determine whether intervention participants significantly increased their participation in physical activity between baseline and 9- and 18-weeks. Within-group analyses will also be conducted to determine whether participants improved in depressive symptoms, positive and negative affect, and physical activity between baseline, immediately following Fit & Strong! participation, and 2 months post-Fit & Strong! participation. Finally, the Baron and Kenny Causal Steps approach [Baron and Kenny, 1986] will be used to determine whether change in physical activity between baseline and immediately post Fit & Strong! mediates the decrease in depressive and positive and negative affect. A process evaluation will be conducted to measure aspects of program implementation including fidelity, intervention dose received, participant attrition, and program acceptability ratings. [Washburn et al., 1993; Miller et al., 1992; Bellamy, 1989; Hughes et al., 1991; Resnick and Jenkins, 2000] See Appendix C. [Maust et al., 2013; van Loon et al., 2013]

C 6.8. Data and Safety Monitoring Plan

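### C 6.7 names no intervention-versus-wait-list contrast for physical activity, so Hypothesis 3 could be judged on a within-arm change that includes any change shared by both arms

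*Combined protocol and SAP*

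**What the plan says.** All references are to the combined protocol and SAP.

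- **Design (C.1).** Up to 20 people are randomised to the program, and "up to 20 individuals will be randomly assigned to a crossover wait-list group". The wait-list starts the program at week 10 and finishes its outcome measures before then.
- **Aim 3 (Section A)** concerns affect, depressive symptoms and "maintenance of physical activity between groups at baseline, and 9- weeks".
- **Hypothesis 3 (Section A):** "Participants randomly assigned to the intervention arm will demonstrate an increase in physical activity at 9- weeks", judged by medium to large effect sizes. No comparator is stated. Hypothesis 2, on mood and affect, does name the wait-list as comparator.
- **C 6.7, general sentence:** "Between-group analyses will be conducted to determine whether significant changes occur in the outcomes between baseline, 9- and 18-weeks". It names no model and no list of outcomes. C.6.3 counts physical activity among the questionnaire outcomes.
- **C 6.7, next sentence:** a "mixed-effects model will be used to determine whether intervention participants significantly increased their participation in physical activity", over baseline, 9 weeks and 18 weeks. This is the only model named for activity as an outcome. No arm term, arm-by-visit term or comparator is given.
- **C 6.7, next sentence again:** "Within-group analyses will also be conducted to determine whether participants improved in depressive symptoms, positive and negative affect, and physical activity".
- **C 6.7, mediation:** the causal-steps approach asks whether "change in physical activity between baseline and immediately post Fit & Strong! mediates" the mood and affect changes. The exposure variable is not stated.

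**The concern.** Activity is both the outcome of Hypothesis 3 and its proposed mediator. Between baseline and Week 9 it could rise in both arms for reasons unrelated to the program: repeated self-report, season, the act of volunteering for an exercise study, and regression to the mean after entry was limited to people exercising less than 150 minutes a week (C.4.1). Randomisation to a wait-list is there to remove such change, but only if the analysis uses the contrast.

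If Hypothesis 3 is judged as worded, a positive result would not show that the program raised activity. The mediation claim needs the effect of arm on activity as its first link, and C 6.7 does not say that arm is the exposure.

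**Working it through.** **1. Which test decides Hypothesis 3?** The passages can be set side by side.

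| Place | Points to |
|---|---|
| Aim 3 | between groups |
| C 6.7, general between-group sentence, with C.6.3 listing activity as an outcome | between groups, but no model or term |
| Hypothesis 3 | change in the intervention arm, no comparator |
| C 6.7, mixed-effects sentence | change in intervention participants, no comparator |
| C 6.7, within-group sentence | within group, stated as additional |

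No sentence ranks these, and no sentence writes down an arm-by-visit term for activity.

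**2. What each test estimates.** Let s be the change shared by both arms and p the program effect.

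- Within-arm change: expected value p + s.
- Difference in change, intervention minus wait-list: (p + s) − s = p.

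**3. Size if the one-arm reading is followed.** The plan states no power, alpha, SD or sample-size derivation, so there is no figure to reproduce.

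Inputs from the documents: 20 per arm (C.1) and 33% non-completion (C.5.2), so 20 × 0.67 = 13.4, taken as 13.

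Assumptions: two-sided 5% test; two visits; SD 1 at both visits in both arms; correlation r = 0.5, range 0.3 to 0.7; p = 0; s = 0.2, 0.3 or 0.5 SD.

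- SD of change = √(2(1 − r)) = √(2 × 0.5) = 1.
- The one-arm paired test has noncentrality s√n / SD of change. For s = 0.5 and n = 20 this is 0.5 × 4.472 = 2.236, against a critical t of 2.093 on 19 df, giving a rejection probability of 56%.

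| Shared rise, no program effect | One-arm test, n = 20 (r = 0.3 to 0.7) | One-arm test, n = 13 (r = 0.3 to 0.7) |
|---|---|---|
| 0.2 SD | 14% (11–19%) | 10% (8–13%) |
| 0.3 SD | 25% (19–37%) | 17% (13–25%) |
| 0.5 SD | 56% (43–78%) | 38% (29–57%) |

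Simulation agrees to within about one percentage point. In the same simulations (shared rises of 0.3 and 0.5 SD) the two-sample test on change, which equals the arm-by-visit test with two visits, rejects in 4.7% to 5.3% of trials.

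**4. The effect-size criterion has the same problem.** With p = 0, the expected standardised within-arm change is s / 1. A shared rise of 0.5 SD would on average reach a medium effect, taking medium as 0.5, with no program effect at all.

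**5. What the randomised contrast gives up** (r = 0.5, no shared change).

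| True effect | n per arm | One-arm power | Between-arm power |
|---|---|---|---|
| 0.5 SD | 20 | 56% | 34% |
| 0.5 SD | 13 | 38% | 23% |
| 0.8 SD | 20 | 92% | 69% |
| 0.8 SD | 13 | 75% | 50% |

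The 95% half-width at 20 per arm is 2.093/√20 = 0.47 SD within arm, and 2.024 × √(2/20) = 0.64 SD between arms. At 0.5 SD, adjusting for baseline raises between-arm power to about 42% (n = 20) or 28% (n = 13).

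**The case against.** The strongest reply is that the plan never excludes the wait-list. Aim 3 is explicitly between groups. The sentence just before the mixed model promises between-group analyses of the outcomes at the same time points, and C.6.3 makes activity an outcome. The sentence just after it adds within-group analyses that name activity, which would be redundant if the mixed model were already within-arm. All of this stands. A reader might infer that the wait-list is left out of the activity model, or write that model as a single-arm equation. The documents support neither: C 6.7 is silent on the model's terms and on who is included.

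A reader might also infer that the mediation analysis cannot estimate the effect of arm on activity, because the wait-list has no measurement just after the program. That is too literal. C.3 pays wait-list participants for a post-test as well, and if arm is the exposure, causal steps regresses activity change on arm. The exposure is unstated, which is a smaller fault.

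Two further points are fair. This is a 40-person pilot with an exploratory Aim 3. And the 18-week part of the sentence could only be within-arm, which may explain some of its wording.

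None of this supplies the missing contrast. The general sentence gives no model, term or outcome, and nothing says that it, and not the sentence matching the hypothesis, decides Hypothesis 3.

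**Conclusion.** The point holds as a gap in specification with a real risk attached; it is not an established one-arm analysis. C 6.7 states no intervention-versus-wait-list contrast for activity, its named model reads as within-arm, and Hypothesis 3 lacks the comparator that Hypothesis 2 has. Aim 3 and the general sentence conflict with that reading.

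The false-positive rates of 14% to 56% (20 per arm) and 10% to 38% (13 per arm) apply only if the one-arm reading is followed, and only under the assumed shared rise of 0.2 to 0.5 SD, correlation of 0.5, equal SDs and two visits. The documents give none of these quantities. What needs no assumption is that the within-arm estimate includes any shared change and the randomised contrast does not. The change should be made, and is proportionate to a pilot because it is a matter of wording.

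**What to change.** 1. **C 6.7, activity sentence.** State that physical activity is analysed in all randomised participants with a mixed-effects model including arm, visit and arm-by-visit, and that Hypothesis 3 is judged on the Week 9 intervention-minus-wait-list difference in change, with its 95% CI.
2. **Hypothesis 3.** Add the comparison with the wait-list to the activity part.
3. **C 6.7, mediation sentence.** Name randomised arm as the exposure, and activity change from baseline to Week 9 in both arms as the mediator.
4. **18 weeks.** Label the intervention-arm change, and any 18-week result, as descriptive and within-arm only. No randomised contrast exists then, because the wait-list starts the program at week 10 and completes its outcome measures before that.
5. **Measure.** Name the activity measure (for example PASE) and confirm that it is repeated at Week 9 in both arms. C2.5 repeats only the questionnaires shown in bold in C.6.3, and bold type is not preserved in the text available for this review.

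**Cost.** Edits to C 6.7 and Hypothesis 3. C.1, C2.5 and C.3 already provide for baseline and post-test assessment, so no new visits or participants are needed, subject to item 5. The interval will be wider and the power lower than the one-arm test appears to offer.

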C2.3. Exercise Intervention. Participants will be invited back to Oakwood Shores for an 8-week physical activity/behavior change intervention. The intervention will consist of the Fit and Strong! program adapted to address the impact of exercise on enhancing positive affect and reducing negative affect and depressive symptoms. Exercise classes will meet three times per week for 90 minutes per session for eight weeks. Each class is divided into 60 minutes of strength training, flexibility, and cardiovascular exercise and 30 minutes of group education/discussion, which has been adapted to include affect-oriented content. An outline of education topics for each of the 24 sessions can be found in Section C.7. Two sessions of Fit and Strong! will be delivered as part of the study; each will be limited to 20 participants. Classes will be taught by certified exercise instructors who will undergo 8-hours of training on the Fit & Strong! Program. The instructor will be trained to deliver depression specific content by a clinical psychologist Program fidelity will be monitored with the Fit and Strong! Plus Implementation Checklist and observation of the intervention by study investigators during one Fit & Strong class per 8-week session. During the intervention, participants will complete a medication adherence and group cohesion measure at baseline, 4 weeks, and 8 weeks.

C2.4. Debriefing Session: Following the intervention, a debriefing session will be held with all intervention participants. This session will be used to adapt Fit & Strong! for future study, addressing issues around affect and treatment effectiveness.

C2.5. Post-Intervention Measures. During Week 9, participants will undergo the same interview, self-report questionnaires (only those bolded in section C.6.3), mobility assessment, and

neuropsychological tests they completed during the baseline visit. Participants that were involved in the MRI testing component will also undergo the same testing for post-intervention results.

C.3 Subject Payment

All participants enrolled in the study (intervention and crossover wait list group) will be paid \$20 upon completion of their baseline interview and \$35 upon completion of their post-test. Participants will be paid in cash. Participants involved in the MRI testing will be paid \$50 in cash upon completion of the scan pre-intervention and post-intervention (\$100 total).

C.4 Entry Criteria for Studies

C.4.1 Inclusion Criteria:

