Exercise Assessment and Screening for You (Resnick, 2008) A self-report questionnaire assessing conditions that might prohibit someone from safely engaging in physical activity (2 minutes).

Six-Item Screener: (Callahan et al., 2002) A brief screen for cognitive impairment and dementia that includes three orientation items (year, month, day of the week) and delayed recall of three items. When a cut-off score of ≤ 1 error is used for diagnosing dementia, sensitivity is reported as 100.0 for community-dwelling elders. (2 minutes)

Patient Health Questionnaire (PHQ-8): A self-report questionnaire assessing symptoms of depression and appropriate for use when a clinician is not involved in the assessment.

C.6.2 Clinical Interview (Approximately 15 minutes)

World Health Organization Disability Assessment Scale (WHO-DAS-II; World Health Organization, 2000). A clinician-administered measure of functioning in six-domains (15 minutes).

C.6.3. Self-Report Questionnaires (approximately 50 minutes)

The composite list of questionnaires includes the following outcomes: health and disability status, depression and affect, physical activity, sleep and fatigue, falls, history, and balance confidence, stress and social/emotional well-being, mobility, and cognitive functioning.

Physical Activity Scale for the Elderly (PASE) [Washburn et al., 1993]. A measure of weekly physical activity (5 minutes).

Western Ontario and McMaster University Osteoarthritis Index [Bellamy et al., 1989]. Set of standardized questionnaires used to collect data on arthritis-specific symptoms using 24 parameters (5 minutes)

Self-Efficacy for Exercise Scale [Resnick and Jenkins, 2000]. A self-report questionnaire developed for older adults addressing expectations around self-efficacy regarding the ability to continue engaging in exercise in the face of hurdles to exercise (3 minutes).

Chronic Conditions: GERI-AIMS: Checklist of chronic medical conditions (3 minutes)

Cardiovascular Risk Factors Questionnaire: Adapted from the Guidelines of the American College of Sports Medicine, ACSM (2000),_A brief screening to determine subjects cardiovascular risk factors (5 minutes).

The Established Populations for the Epidemiologic Study of the Elderly (EPESE) Questionnaire: A Likert-type scale for rating of ability to complete basic and instrumental activities of daily living. (5 minutes)

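### Mediation under exploratory Hypothesis 3 is to be tested only by Baron-Kenny causal steps, with no planned indirect-effect estimate or interval

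*Combined protocol and SAP*

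**What the plan says.** Hypothesis 3 (A. Specific Aims) expects the intervention arm to become more active by week 9, and expects the improvement in affect to be mediated by that increase. Aim 3, to which it belongs, is worded as exploration.

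Section C 6.7 gives mediation one sentence. It says that "the Baron and Kenny Causal Steps approach" will be used to establish "whether change in physical activity between baseline and immediately post Fit & Strong! mediates the decrease in depressive and positive and negative affect". The outcomes are therefore depressive symptoms, positive affect and negative affect. The sentence names no exposure, lists no steps, and mentions no product of coefficients, standard error or interval. The other analyses in C 6.7 (repeated measures ANOVA, the mixed-effects model, within-group comparisons) are not mediation methods.

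C.1 plans 40 participants, up to 20 per arm. C.5.2 expects 33% not to complete. No alpha, power, SD or path size is stated anywhere, and effects are described only as medium to large.

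**The concern.** Standard causal steps is a chain of significance tests: total effect of arm on outcome, arm on mediator, and mediator on outcome given arm. It ends in a yes or no. In a small pilot the first test often fails by chance, and mediation is then recorded as unsupported even if both paths look as hypothesised.

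That sits badly with Hypotheses 2 and 3, which are to be judged by effect size. An observed medium effect could satisfy Hypothesis 2 and still close the first step for Hypothesis 3. What a pilot can usefully pass on is an estimate of the indirect effect and its uncertainty, and the plan commits to neither. No primary conclusion is at stake.

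**Working it through.** There is no planned figure to reproduce, because the documents give no sample-size or power calculation.

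**Inputs from the documents.** 40 enrolled (C.1). 33% non-completion (C.5.2), so 40 × 0.67 = 26.8, about 27 completers, taken as 13 and 14 per arm.

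**Assumed inputs.** Two-sided alpha 0.05. Total effect d = 0.5 to 0.8 SD and arm-to-activity path a = 0.5 to 0.8 SD, as a reading of medium to large. Activity-to-outcome path b = 0.3 to 0.5.

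**Step 1: the total-effect test alone.** The smallest observed d that reaches significance is t(0.975, df) × √(1/n₁ + 1/n₂).
- 20 per arm: 2.024 × √(1/20 + 1/20) = 2.024 × 0.316 = 0.64.
- 13 and 14: 2.060 × √(1/13 + 1/14) = 2.060 × 0.385 = 0.79.

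Power comes from the noncentral t with noncentrality d / √(1/n₁ + 1/n₂).
- 27 completers: d = 0.5 gives 0.5/0.385 = 1.30 and power 24%; d = 0.8 gives 2.08 and power 51%.
- 40 completers: d = 0.5 gives 0.5/0.316 = 1.58 and power 34%; d = 0.8 gives 2.53 and power 69% (70% in simulation).

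So after the expected dropout the first step fails about half the time or more, even when a medium to large effect is real.

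**Step 2: detecting mediation.** Model: M = a·arm + e and Y = c′·arm + b·M + e, with unit residual SDs and c′ set so that the total effect equals d. Causal steps counts as detection when the total effect, a and b are all significant. The alternative counts as detection when a 95% percentile-bootstrap interval for a·b excludes zero. Both adjust for the baseline mediator and the baseline outcome (assumed retest correlation 0.7, effects in residual-SD units). Ranges cover d = 0.5 to 0.8.

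| Completers | a, b | Causal steps | Bootstrap interval |
|---|---|---|---|
| 27 | 0.5, 0.3 | 2-4% | 6-7% |
| 27 | 0.8, 0.5 | 9-17% | 29% |
| 40 | 0.5, 0.3 | 5-10% | 13% |
| 40 | 0.8, 0.5 | about 20-40% | 55% |

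Figures move by a point or so between simulation runs. At 27 completers the better method still misses about 71-94% of true effects (100 − 29 and 100 − 6).

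**Step 3: where the gain comes from.** A joint test of a and b without the total-effect requirement does about as well as the bootstrap. Adjusted, at 27 completers with a = 0.8 and b = 0.5, the bootstrap detects 0.278 and 0.312 against 0.283 and 0.318 for the joint test (two total-effect settings). Nearly all of the gain is from dropping the first step. The bootstrap's own contribution is the interval.

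**Step 4: how wide the interval is.** In outcome SDs, true indirect effects run from 0.5 × 0.3 / √(1 + 0.3²) = 0.14 to 0.8 × 0.5 / √(1 + 0.5²) = 0.36. In the unadjusted version of the model, median interval width is 0.69-0.93 SD at 27 completers and 0.53-0.73 SD at 40.

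**Step 5: bootstrap error rates.** Unadjusted coverage was about 92-94%. False positives with one path null stayed at or below 5% when the other path was 0 to 0.8, and reached 6-7% when it was very strong (a = 1.2 or b = 1.0).

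**The case against.** Several objections have force.

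- **The total-effect requirement is not protocol text.** C 6.7 lists no steps, so the requirement is inferred from the standard form of the named method. That stands, and steps 1 and 2 are conditional on it. The omission of any planned indirect effect or interval is not.
- **A reader might infer that causal steps makes an estimate unobtainable.** It does not. Its regressions yield a and b, so a·b could be computed from the same data. The gap is in what the plan commits to report.
- **The power gain is not uniform.** If medium to large means raw SDs, baseline adjustment adds precision and the gap narrows. At 40 completers with d = 0.8, two runs gave 21% v 21% and 25% v 26% for the weaker paths (causal steps first), and 70% v 76% and 76% v 85% for the stronger. It remains at d = 0.5 (39% v 73% for the stronger paths at 40) and at 27 completers with d = 0.8 (36% v 48%, stronger paths).
- **An interval several times wider than the effect informs planning little.** True, but it shows how little is known, which a bare negative verdict conceals.

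A reader might also infer that the activity and mediation analyses are confined to the intervention arm. The mediator is timed to the end of the program, C.1 says "The wait-list group will complete all of their outcome measures before they begin the intervention", and C 6.7 says "A mixed-effects model will be used to determine whether intervention participants significantly increased their participation in physical activity". The documents do not support that inference. Hypothesis 3 implies randomised arm as the exposure. C2.5 sets the repeat measures "During Week 9, participants will undergo the same interview, self-report questionnaires (only those bolded in section C.6.3", and C.3 says "All participants enrolled in the study (intervention and crossover wait list group) will be paid" for baseline and post-test, which points to a week-9 assessment in both arms. C 6.7 adds "Between-group analyses will be conducted to determine whether significant changes occur in the outcomes", C.6.3 lists physical activity among those outcomes ("The composite list of questionnaires includes the following outcomes: health and disability status, depression and affect, physical activity"), and Aim 3 is framed between groups. These are matters of wording to clarify, not defects.

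**Conclusion.** The point holds, as a minor one. The plan names causal steps as its only mediation method and plans no indirect-effect estimate or interval. In standard form, the first step would pass only about 24-51% of the time at 27 completers and 34-70% at 40 when the assumed effects are real, so a negative mediation result would say little about the paths.

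Replacing it roughly doubles or triples detection at 27 completers in the adjusted residual-SD scenarios, but from a very low base, and the advantage can almost vanish at 40 completers with a large raw-SD effect. It would be wrong to conclude that the change makes the trial adequately powered for mediation, or that the feasibility or efficacy aims are affected. All magnitudes depend on assumed alpha, effect sizes, path values and retest correlation. That no indirect effect or interval is planned can be read directly from C 6.7.

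**What to change.** Replace the causal-steps sentence in C 6.7. For each outcome it covers (positive affect, negative affect, depressive symptoms), report the indirect effect of randomised arm through baseline-to-week-9 change in physical activity. Estimate it using both arms as a·b, adjusted for baseline PASE and the baseline value of the outcome, with a percentile-bootstrap 95% interval, whether or not the total effect is significant. Label it exploratory: activity is not randomised, and mediator and outcome are measured at the same visits.

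While editing, name arm as the exposure, give the mediator's time point as week 9 for both arms, and write the activity model with an arm-by-time term (or week-9 PASE by arm, adjusted for baseline).

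The cost is SAP wording and a little more analysis, with no new data provided PASE is repeated at week 9. Aim 3 implies that it is, but the bolding that marks the repeated questionnaires is not visible in the text, so this should be confirmed. PASE is the natural choice of mediator measure, although C 6.7 does not name it. The downsides are coverage slightly under 95% and false positives of up to about 7% when one path is null and the other very strong. Both are tolerable for an exploratory estimate.
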